 28 For example for question n° 2: 1 point if predefined keyword present; 0,5pt if partial keyword  
 29 but general concept correct; 0 pt otherwise.

30  
 31 The final score can vary from 0 (no knowledge) to 17 points (excellent knowledge).  
 32 The questionnaire has never been used in an experimental context or for psychometric  
 33 analysis. There is no threshold to say that a patient has good knowledge or not.  
 34 It was developed by an internal pharmacist and an assistant pharmacist trained in TVE. It is  
 35 based on educational objectives derived from educational sessions with patients and meetings  
 36 with two patient partners from the HUG (Appendix 2). It was previously evaluated with them  
 37 and on three occasions with a group of hospitalized heart failure patients (10 patients per  
 38 version of the questionnaire).

39  
 40 To determine a first basic level of knowledge of the heart failure patients hospitalized at the  
 41 HUG, the final version of the questionnaire was tested with 10 patients who had not received  
 42 any educational intervention. This analysis shows that:

- 43 • The average baseline score is 7.95 pts out of 17.00pts (with a standard deviation of  
 44 2.67) or 46.76% of correct answers;
- 45 • The median score of 8.25pts out of 17.00 pts (min. 4; max. 13) or 48.53% of correct  
 46 answers.

47  
 48 In this clinical study, we wish to assess the level of knowledge of the intervention group before  
 49 the teaching interview, directly after the teaching interview, and at 1 month after the  
 50 participant's discharge from the hospital.

51 This study includes a control group in order to evaluate the real effect of the therapeutic  
 52 teaching intervention. The level of knowledge of the control group will be evaluated at inclusion  
 53 for the pre-test and at 1 month after hospitalization for the post-test.

54

1  
2 Secondary endpoints included differences in medication belief and adherence scores and the  
3 difference in the rate of unplanned care use between the two groups at 1 month post-  
4 hospitalization.

5  
6 They also focused, for the intervention group, on the difference in belief and therapeutic  
7 adherence scores between the period before the educational intervention during  
8 hospitalization and the period following this intervention, i.e., one month after hospital  
9 discharge.

10 Four additional endpoints will be assessed after the pharmaceutical intervention with the study  

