11 population in the intervention group.

- 12
- 13 • Satisfaction with the pharmacist's teaching and services
- 14 • The patient's experience and feelings upon returning home
- 15 • The rate of re-hospitalization and emergency department visits within 30 days of  
16 discharge.
- 17 Death rate at 1 month after hospitalization

18 Two parameters will be measured, from a pilot project point of view, only with the participants  
19 of the intervention group who agreed to install and use the CardioMeds® mobile application  
20 after hospitalization.

- 21 • The use and usability of a specific mobile smartphone application for heart failure  
22 patients (CardioMeds®).
- 23 • Self-care skills learned through information delivered on the mobile app.

24  
25  
26 **Beliefs about medicines** will be assessed using the Beliefs about Medicines Questionnaire  
27 (BMQ) developed by Horn et al. (57). This questionnaire has been validated in many chronic  
28 diseases, including cardiac pathologies (58–61). It is composed of 18 questions that are  
29 evaluated according to a 5-point Likert scale ranging from 1 "strongly agree" to 5 "strongly  
30 disagree". The questionnaire is separated into 2 parts. A specific BMQ part with 10 items  
31 measuring specific beliefs about the prescribed treatment, in terms of its necessity and worries  
32 or concerns, and a general BMQ part with 8 other items measuring general beliefs about  
33 medicine, including the perception of harm and overuse. This second part will not be evaluated  
34 in this project.

35 The specific BMQ is composed of two 5-question subscales. It is presented in Appendix 3.  
36 Five items assess patients' representations of their medical prescription, or more precisely,  
37 their beliefs about the need to adhere to the prescribed drug treatment (= specific need) and 5  
38 items measure beliefs about the risk of dependence and side effects caused by the treatments  
39 (= specific concerns).

40 Scores range from 5 to 25 points for both subscales. The higher the score for specific necessity,  
41 the more it means that the patient has a strong perception that he or she needs the medication  
42 to be healthy and live. For specific concern, the higher the score, the more concerned the  
43 patient is about a potential negative effect from taking the medication. A third score can be  
44 calculated by subtracting the specific concerns from the specific needs. This gives a score of  

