45 -20 to +20. A positive value means that the need for the treatment exceeds the concerns about  
46 taking it. This questionnaire has adequate internal consistency in a cardiac population  
47 (Cronbach alpha = 0.76) and correlates well with other measures of beliefs (57). The validated  
48 French version is used in this project. (62).

49  
50 **Medication adherence** will be assessed by means of a self-report questionnaire entitled  
51 "Three-item self-report scale (63). This questionnaire consists of 3 questions: one that  
52 evaluates the number of days that medication was forgotten in the last month, one that  
53 evaluates the frequency of taking medication as prescribed by the doctor, and the third that  
54 measures the patient's level of competence in taking medication correctly. Responses are

1 converted to a scale of 0 to 100 (0 being the lowest adherence and 100 the highest). An  
2 average of the three responses is used to assign the adherence score. This questionnaire has  
3 a high internal consistency (Cronbach alpha = 0.87) and correlates well with other measures  
4 of adherence (POC and MEMS). (63–65). We translated this questionnaire into French  
5 (Appendix 4) according to the methodology proposed by de Sousa et al. (66).  
6

7 Study participants' **satisfaction** will be assessed using a 13-question questionnaire (Appendix  
8 5) after the teaching interview to evaluate the usefulness and quality of the teaching service.  
9 A second satisfaction questionnaire consisting of 5 questions will be sent at 1 month after  
10 hospital discharge to assess the patient's overall satisfaction with the pharmacist's care  
11 (Appendix 6). These results will allow us to determine whether this new service should be  
12 continued and to identify its strengths and weaknesses.  
13

14 The patient's **experience and feelings** upon returning home will be assessed during a  
15 telephone call between D3 and D7 after the patient's discharge from the hospital. The objective  
16 will be to identify the patient's needs, their feelings about going home, what they liked, what  
17 they missed. It will also be assessed if the patient has obtained a treatment card, has organized  
18 to go and get his medication and has organized to integrate it into his daily life. A list of  
19 medications will be collected from the patient. The questions asked are presented in Appendix  
20 7.  
21

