51 application on patients' level of empowerment in their care.  
52  
53

[figure not shown]
1 During hospitalization, the four questionnaires (knowledge, beliefs, therapeutic adherence,  
2 and satisfaction) will be sent to the participants in paper or electronic format (on a tablet)  
3 according to the patient's wishes by the pharmacist investigator or the research assistant.  
4 These questionnaires will be sent again to the participants at 1 month after discharge from  
5 hospital, as well as the two questionnaires for the participants using CardioMeds®. They will  
6 be sent either by e-mail or by post to be completed by the patient and returned to the  
7 investigator. In the event that these questionnaires are not returned, they will be addressed  
8 orally during a telephone interview by a research assistant.

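### Section 3.2 contradicts itself on BMQ scoring: items run from 1 = strongly agree to 5 = strongly disagree, yet higher scores are read as more need and more concern, and no recoding step is stated

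*Combined protocol and SAP*

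**What the plan says.** The description of beliefs about medicines in section 3.2 makes these statements:

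- **Response format.** The items are "evaluated according to a 5-point Likert scale ranging from 1 'strongly agree' to 5 'strongly" disagree.
- **Structure.** "The specific BMQ is composed of two 5-question subscales. It is presented in Appendix 3". One subscale covers the need for treatment and the other covers concerns about it.
- **Need.** "Scores range from 5 to 25 points for both subscales. The higher the score for specific necessity", "the more it means that the patient has a strong perception that he or she needs the medication".
- **Concerns.** "For specific concern, the higher the score, the more concerned the" patient is about harm from the medication.
- **Differential.** Concerns are subtracted from need, giving -20 to +20. "A positive value means that the need for the treatment exceeds the concerns about" taking it.

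No recoding step appears in section 3.2, in the belief-assessment part of section 4.3, or in sections 5 and 5.1. Table 2 lists the need, concern and differential scores at pre-test (items 58-60) and at 1 month (items 82-84), and gives their origin only as a calculation. Item-level answers are also recorded (items 57 and 81).

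The scores are used in two comparisons. Sections 5 and 5.1 compare the two groups by Student's t test. Section 3.2 adds a before/after comparison: "They also focused, for the intervention group, on the difference in belief and therapeutic" adherence scores.

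**The concern.** The anchors and the score interpretations point in opposite directions. Under the stated anchors, a patient who agrees strongly with every need item collects the lowest codes, and so gets the lowest total. The same section reads a low total as weak perceived need.

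Beliefs are a named secondary outcome and their direction matters. Section 7.1 says that if knowledge, beliefs and adherence improve, the interviews could be offered to all heart failure inpatients. If the stated codes are summed, a gain in perceived need would be reported as a loss, and a patient whose need outweighs concern would be classed the other way round. Section 8.3 has prepared data transferred to a statistician in a separate unit. Someone working from section 3.2 could code in either direction and cite the protocol for it.

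**Working it through.** **Inputs, all from section 3.2:** five items per subscale; codes 1 to 5 with 1 = strongly agree; differential D = need N minus concerns C; higher scores read as more need or more concern. One assumption is added: agreeing with an item expresses need or concern. The subscale descriptions imply this, but the item wording is in Appendix 3.

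**Step 1. Reproduce the stated ranges.** Subscale: 5 × 1 = 5 to 5 × 5 = 25. Differential: 5 - 25 = -20 to 25 - 5 = +20. Both match the protocol. Both are also the same whether or not the items are recoded, so the ranges do not settle the direction.

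**Step 2. Extreme case.** Take a patient who strongly agrees with all need items and strongly disagrees with all concern items.

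| Scoring | Need | Concerns | Differential |
|---|---|---|---|
| Stated codes summed | 5 × 1 = 5 | 5 × 5 = 25 | -20 |
| Recoded as 6 - x, then summed | 5 × 5 = 25 | 5 × 1 = 5 | +20 |

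Only the recoded row fits the protocol's interpretation. The unrecoded row would be read as least need, most concern, and concern exceeding need.

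**Step 3. General case.** With x' = 6 - x for each item, the recoded subscale is S' = 5 × 6 - S = 30 - S. It equals S only at 15, so 20 of the 21 possible values (5 to 25) change. The differential becomes D' = (30 - N) - (30 - C) = -(N - C) = -D. It equals D only at 0, so 40 of the 41 possible values (-20 to +20) change sign. Example: intended need 20, concerns 12 and differential +8 would be recorded as 30 - 20 = 10, 30 - 12 = 18 and 10 - 18 = -8.

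**Step 4. Effect on the tests.** Replacing S by 30 - S in everyone turns a mean difference d into -d and leaves the variances unchanged, so t becomes -t with the same two-sided p-value. A check on simulated scores, 62 per group, gave t = -2.21 and t = +2.21 on 122 degrees of freedom, with p = 0.029 both times. For the before/after comparison, (30 - post) - (30 - pre) = -(post - pre), so +2 points becomes -2.

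**Step 5. Mixed coding.** Steps 3 and 4 assume that every record is treated alike. If some were recoded and others not, the result would no longer be a clean sign reversal, and means, variances and p-values would all be affected.

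**The case against.** The strongest reply is that the two statements conflict only if raw codes are summed, and the protocol never says so outright. It gives a response format and, separately, the meaning of the final scores; reverse coding would reconcile them. The meaning of a high score is explicit, so an analyst who follows it has only one correct coding for a given form. Appendix 3 may show the opposite anchors or a scoring key, and section 3.2 says the validated French version is used. Table 2 is a data-collection list that refers to questionnaire-specific documents for the answers, so its lack of a formula proves little.

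Much of this stands, and it limits the consequence. A reversed result is a possibility that depends on the form and the calculation; it has not been shown to occur. The counts in step 3 follow from any reflection about a midpoint and do not estimate error in this trial. Section 3.2 describes several modes of delivery and does not say that the forms differ in their anchors. Stored item answers would allow any error to be found and corrected.

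The reply does not remove the conflict. The anchors and the interpretation are both protocol text, they disagree unless a recoding step is supplied, and the available text supplies none. For the other scored outcomes the same section does give rules: point by point for knowledge, and a conversion to 0-100 with its direction for adherence.

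**Conclusion.** The concern holds. Section 3.2 leaves the scoring direction of a named secondary endpoint contradictory, and it should be corrected before analysis. If the stated codes are summed, each subscale becomes 30 minus its intended value and every non-zero differential, group difference and before/after change has the wrong sign, with two-sided p-values unchanged. If Appendix 3 carries the opposite anchors or a scoring key and that is what is used, the numerical effect is nil and only the text needs correcting.

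The conclusion rests on agreement expressing need or concern, and on there being no recoding rule outside the available text. The primary knowledge analysis and the sample size are not affected.

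**What to change.** First check the anchors and any scoring key in Appendix 3 and in the eCRF. In hospital the questionnaires "and satisfaction) will be sent to the participants in paper or electronic format (on a tablet"), and at 1 month they go by e-mail or post with a telephone fallback, so confirm that every mode uses the same anchors and codes. Then:

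- if the form is printed 1 = strongly disagree to 5 = strongly agree, correct the anchors in section 3.2;
- if it is printed 1 = strongly agree to 5 = strongly disagree, keep the anchors and state in section 3.2 that each item is recoded as 6 minus the response before summing.

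In either case, verify the need, concern and differential calculations at pre-test and at 1 month against a few item-level records before analysis.

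The cost is one sentence in section 3.2, a check of the form, and a check of three score calculations at two time points. No data are lost, because the item answers are stored.

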### 9 **3.3 Study design**

10 The design of the clinical study chosen is a parallel randomized controlled trial. This design  
11 will allow us to evaluate the effect of our intervention without the confounding effects and  
12 selection biases inherent in observational studies, which strengthens the internal validity of the  
13 project.

14  
15  
16 The design of the study is schematized and detailed in French only in Figure 1 below.

Figure 1 : Design of the clinical study

### 3.4 Study intervention

The control group will receive the usual care offered by the internal medicine service without the therapeutic education intervention of the pharmacist during their hospitalization.

The intervention will be conducted by the pharmacist investigator with patients in the intervention group. These are heart failure patients with reduced LVEF, polymedicated, hospitalized for cardiac decompensation in the 10 general internal medicine units of the HUG. They will benefit from the usual medical care. The intervention will consist of an educational pharmaceutical interview associated with a second interview to prepare for hospital discharge (pre-discharge interview), followed by a telephone call a few days after hospital discharge.

The therapeutic education intervention that the patient will receive will be structured in three parts:

1. The first part consists of a 60-90 minute interactive edutainment session that will take place in the patient's bed. It will be carried out from the 3rd day of admission for a cardiac decompensation. The teaching is structured in two subparts, which will allow it to be carried out in one or two sessions if necessary to reduce its duration and preserve the patients' level of concentration. One or two appointments will be scheduled with the patient to ensure that they are available throughout the interview.

The teaching will address 3 themes related to the disease of heart failure: the pathology, the drugs to treat it and the self-care and self-monitoring actions to adopt. A pedagogical scenario has been designed to serve as a detailed description of the teaching and as a teaching guide for the pharmacist trainer. It is presented in the appendix (Appendix 11).

The teaching is standardized and can be used for all patients, regardless of their level of knowledge. Indeed, the elements and the games used are flexible according to the skills of the participants. The trainer will be able to vary his level of investment according to their needs, their wishes and their skills.

Below is a brief description of the elements used in this interview:

- The pathology will be approached by means of an existing video developed by the Cardiology Service of the HUG explaining the definition, the mechanism of the disease, its effects, its complications and the causes. This video will be viewed by the patient after having answered the pre-test questionnaires. After viewing the video, a discussion with the patient, using active communication techniques (open questions, rephrasing,) and tools such as photolanguage, picture cards, and card games, will allow the patient to contextualize his or her disease, and to discuss the notions of chronicity of the disease, cardiac decompensation, and associated symptoms.
- Each of the patient's medications prescribed for heart failure during hospitalization will be visualized and explained (role, mechanism of action) as well as their benefits. A game board will be used as a teaching aid. It will allow the patient to associate images of his medication boxes in the different therapeutic classes. Real-life scenarios will be used to address the risks involved in forgetting to take medication. A discussion on the notion of chronicity of medication intake and the continuous adjustment of medication doses will be initiated. Finally, the main adverse effects of some therapeutic classes will be reviewed by means of a quiz and a discussion on the information given on the package inserts of medications.
- The proper daily actions that a heart failure patient should follow to assess the progress of his or her disease and know when to seek medical attention will be reviewed in subpart 1. Behaviors in case of medication-related side effects and forgetting to take medication will also be discussed in sub-section 2.

2. The **second part of the intervention is** characterized by a discharge interview between the pharmacist and the patient. It will be conducted between 1-2 days prior to discharge from the General Internal Medicine Service, whether the patient is going home or being transferred for a rehabilitation care stay. Its purpose is to prepare the patient for discharge from the hospital, his or her future treatment plan and self-care practices. It differs from the discharge interview conducted by the physician who is in charge of handing out the official discharge documents (discharge notice with the next medical appointments planned or to be organized, a prescription for medication and a treatment plan)

The pharmacist will ensure that the following elements of continuity of care are established:

- the patient has a community pharmacy where he/she can collect his/her medication and which can follow him/her;
- the organization of the medication at home is adapted to the needs and lifestyle of the patient;
- Resource persons are identified when needed.

He will give the patient a document in the form of a "memory card" that will highlight the important key points of the heart failure medication education. It is the patient himself, during this interview, who will take care to complete this document to visualize his current list of heart failure medications and the adverse effects to be followed. A flyer entitled "control of heart failure" developed by the Cardiology Service of the HUG will be given to them so that they have a reference scale to rely on to evaluate their symptomatology and the need to consult or not and to remember the good self-care gestures to adopt at home. At this stage, the patient will also be asked if he/she would like to have a treatment card in paper format (made by the internal physician) or in digital format available on a smartphone (CardioMeds®).

In case the patient wishes to benefit from this digital tool, the CardioMeds application® will be presented and installed by the pharmacist.

3. The **third step of the intervention** consists of a telephone call to the patient between D3 and D7 after discharge from hospital by the pharmacist (including patients who have stayed in a rehabilitation unit). This call will allow the pharmacist to ensure that the patient has picked up their medications and is clear on their treatment plan. It will also serve to ensure that the patient is not showing signs of decompensation of their heart failure. He or she will be available for any questions the patient may have regarding his or her health and will refer the patient to the appropriate resource people if necessary.

The tools used to create the teaching interview and the pedagogical scenario were developed by a clinical pharmacist in general internal medicine, inspired by existing tools for heart failure patients and helped by the information needs of heart failure patients at the HUG, the opinion of two patient partners, and the opinion of health professionals at the HUG (clinical pharmacists, cardiologist, nurse).

The scenario was validated by a group of experts composed of a clinical pharmacist specialized in TPE, a cardiology nurse specialized in the follow-up of heart failure patients, a cardiology assistant physician in charge of the heart failure and rehabilitation unit, as well as heart failure patients and two patient partners. The teaching was tested with three pharmacy students and two partner patients, one of whom had heart failure.

The research project was validated by two assistant physicians: the assistant physician of the Department of General Internal Medicine and the cardiologist in charge of the heart failure unit of the HUG.

